5.4.4. Medical History

Medical history is defined as any condition, with the exception of the study indication, that the patient may have had prior to enrollment in the study, including any chronic conditions diagnosed prior to entry in the study.

Medical history will be coded using the Medical Dictionary for Regulatory Activities (MedDRA) [most recent version at time of DB lock] and will be presented by System Organ Class (SOC) and Preferred Term (PT) and total. The SOCs and PTs are to be sorted by descending SOCs and descending PTs in the total column.

Medical history records will be summarized for the ASaT population by overall as follows:

- The number and percentage of patients with at least one medical history record will be presented.
- The number and percentage of patients with at least one medical history record within each primary SOC and PT will be presented. The summary will be sorted using the descending order for SOC and using descending order of overall numerical counts for PT. Where terms tie, these will be sorted alphabetically.

Medical history records will be listed by-patient and within-patient by medical history start date for the screened population.

5.4.5. Prior and Concomitant Medications

All medications will be coded using the Format B3G [most recent version at time of DB lock], Anatomical Therapeutic Chemical (ATC) Classification codes.

Prior medications and concomitant medications are defined as follows:

- Prior medication is defined as those taken prior to the first dose with a stop date and time prior to the start of the Treatment Period.

- Concomitant medications are those with a start date and time on or after the start of the Treatment Period, or those with a start date and time before the start of the Treatment Period and either a stop date and time on or the start of the Treatment Period, or are ongoing at the end of the study.

See [Section 4.2.3](#) for imputation of missing or partial dates for medication.

Prior and concomitant medications will be summarized separately for the ASaT population overall as follows:

- The number and percentage of patients with at least one prior/concomitant medication will be presented.
- The number and percentage of patients with at least one prior/concomitant medication within each Anatomical Group (ATC Level 1), Therapeutic Subgroup (ATC Level 2), and preferred term will be presented. The summary will be sorted using numerical counts by descending order of Anatomical Group, then descending order of Therapeutic Subgroup, then descending order of preferred term in the total column. Where groups or terms tie these will be sorted alphabetically.

Prior medications and concomitant medications will be listed separately for the enrolled population. In the listings the relative start and stop day of prior/concomitant medication use will be calculated relative to the first dose date and time of treatment and will be presented for those patients who received at least one dose of treatment. If the concomitant medication is “Ongoing” it will be indicated as such in the listing and the relative stop day will not be calculated. Only original dates will be presented in the listing even though the relative day may be based on an imputed date.

5.4.6. Prior and Concomitant Procedures

All procedures will be coded using the MedDRA dictionary [most recent version at time of DB lock] and presented by System Organ Class (SOC) and Preferred Term (PT). The SOCs and PTs are to be sorted by descending SOCs and descending PTs.

Prior procedures and concomitant procedures are defined as follows:

- Prior procedure is defined as those done prior to the first dose with a stop date and time prior to the start of the Treatment Period.
- Concomitant procedure are those with a start date on or after the start of the Treatment Period, or those with a start date before the start of the Treatment Period and either a stop date on or the start of the Treatment Period, or are ongoing at the end of the study.

See [Section 4.2.3](#) for imputation of missing or partial dates for procedure.

Prior and concomitant procedures will be summarized separately for the ASaT population overall as follows:

- The number and percentage of patients with at least one prior/concomitant procedure will be presented.

- The number and percentage of patients with at least one prior/concomitant procedure within each SOC and PT.

Prior procedures and concomitant procedures will be listed separately for the enrolled population. In the listings the relative start and stop day of prior/concomitant procedures use will be calculated relative to the first dose date of treatment and will be presented for those patients who received at least one dose of treatment. If the concomitant procedure is “Ongoing” it will be indicated as such in the listing and the relative stop day will not be calculated. Only original dates will be presented in the listing even though the relative day may be based on an imputed date.

5.4.7. Prior Radiation Therapy

Number and percentage of patients having prior radiation therapy will be summarised within each primary SOC and PT for the ASaT, Efficacy, and PP populations as a part of prior non-systemic anti-cancer therapy.

Prior radiation therapy data will be listed for the enrolled population as a part of prior non-systemic anti-cancer therapy.

5.4.8. Prior Anti-Cancer Surgery

Number and percentage of patients having prior anti-cancer surgery will be summarised within each primary SOC and PT for the ASaT, Efficacy, and PP populations by treatment group and overall as a part of prior non-systemic anti-cancer therapy.

Prior Anti-cancer surgery data will be listed for the enrolled population as a part of prior non-systemic anti-cancer therapy.

5.4.9. Prior Systemic Anti-Cancer Therapy

Number and percentage of patients having prior systemic anti-cancer therapy will be summarised within ATC Level for the ASaT, Efficacy, and PP populations by treatment group and overall as a part of prior systemic anti-cancer therapy.

Prior systemic anti-cancer therapy data will be listed for the enrolled population as a part of prior systemic anti-cancer therapy.

5.4.10. Subsequent Radiation Therapy

Subsequent Radiation therapy data will be listed for the enrolled population as a part of subsequent non-systemic anti-cancer therapy.

5.4.11. Subsequent Anti-Cancer Surgery

Subsequent Anti-Cancer Surgery data will be listed for the enrolled population as a part of subsequent non-systemic anti-cancer surgery.

5.4.12. Subsequent Systemic Anti-Cancer Therapy

Subsequent Systemic Anti-Cancer therapy data will be listed for the enrolled population as a part of subsequent systemic anti-cancer therapy.

5.5. Efficacy

Only tumor assessments prior to or at the date of initiation of further-line therapy and using CT scan or MRI will be used for the evaluation of tumor response.

In case of a confirmed response or disease progression, the date of the first tumor assessment evaluated as response or progression will be used for the time-to-event variables.

Up to the first iUPD, the RECIST 1.1 disease response assessment will be derived from the iRECIST response assessment form as follows:

Table 2 Derivation of RECIST 1.1 Disease Response from iRECIST 1.1

iRECIST	RECIST 1.1
iCR	CR
iPR	PR
iSD	SD
iUPD	PD
Non-iCR/Non-iUPD	Non-CR / Non-PD
NE	NE

After the first iUPD, the RECIST 1.1 overall response will no longer be derived.

All efficacy data endpoint will be listed on the enrolled population, with the exception of time to event analyses where the ASaT population will be used.

Overview of Tumor Assessments with a swimmer plot per RECIST 1.1 and iRECIST 1.1 will be displayed graphically for ASaT population.

5.5.1. Primary Efficacy Analysis

The ORR is defined as the proportion of patients with Complete Response according to RECIST 1.1 (CR) or Partial Response according to RECIST 1.1 (PR). ORR will be analyzed in the efficacy population and presented as a point estimate along with 95% Clopper-Pearson CI. Patients with missing data will be considered as non-responders.

To determine the ORR, the BOR (see [Section 5.5.3.1](#)) of each patient will be computed according to RECIST v1.1 criteria.

ORR according to RECIST 1.1 will also be listed for enrolled population.

5.5.2. Sensitivity for the Primary Analyses

Primary efficacy analysis will be repeated for ASaT and PP populations.

Primary efficacy analysis will be repeated where patients with missing data will be excluded from the analysis.

5.5.3. Secondary Efficacy Analysis

5.5.3.1. BOR and iBOR

The BOR and iBOR are defined as the best response from the start of study treatment until the first documented disease progression, death, or start of new anti-cancer therapy. It will be summarized with counts and percentages in the efficacy population and will be repeated for ASaT and PP populations.

This will also be repeated in the efficacy population where patients with missing data will be excluded from the analysis.

Stable Disease according to RECIST 1.1 (SD) and Stable Disease according to iRECIST (iSD) needs to last at least 6 weeks from the start of study treatment, if not, at least one follow-up scan is required to declare stable disease.

BOR according to RECIST and iRECIST as well as the Overall Response will also be listed for enrolled population.

For BOR each patient will be assigned one of the following categories (from best response to worst response): CR, PR, SD, PD, NE:

Step	Condition
Step 1: BOR of CR If a BOR of CR is not determined, Step 2 will be performed.	At least two consecutive determinations of CR more than 4 weeks apart, or if not consecutive, with no other assessment between the two determinations other than unable to evaluate (NE), CR.
Step 2: BOR of PR If a BOR of PR is not determined, Step 3 will be performed.	At least two consecutive determinations of PR or CR, more than 4 weeks apart, or if not consecutive, with no other assessment between the two determinations other than NE, CR, PR.
Step 3: BOR of SD If a BOR of SD is not determined, Step 4 will be performed.	At least one SD assessment (or better), ≥ 6 weeks (≥ 42 days) after baseline; if not, at least one follow-up scan (i.e., consecutive scan) evaluated as SD (or better) is required

	to determine a BOR of SD. If not consecutive scans, with no other assessment between the two determinations other than NE, CR, PR, SD.
Step 4: BOR of PD If a BOR of PD is not determined, Step 5 will be performed.	At least one (i.e., any) PD after baseline.
Step 5: BOR of NE	Measurable disease at baseline, but not all or any target lesions have been evaluated, or if derivation of BOR from Step 1 to 5 does not apply. Non-measurable disease at baseline will also result in BOR of NE.

For iBOR each patient will be assigned to one of the following categories (from best to worst responses): iCR, iPR, immune Stable Disease (iSD), immune Confirmed Progressive Disease (iCPD), immune Unconfirmed Progressive disease (iUPD), or Not Evaluable (NE) at each timepoint:

Step	Condition
Step 1: iBOR of iCR If an iBOR of iCR is not determined, Step 2 will be performed.	At least two consecutive determinations of iCR more than 4 weeks apart, or if not consecutive, with no other assessment between the two determinations other than unable to evaluate (NE), iCR.
Step 2: iBOR of iPR If an iBOR of iPR is not determined, Step 3 will be performed.	At least two consecutive determinations of iPR or iCR, more than 4 weeks apart, or if not consecutive, with no other assessment between the two determinations other than NE, iCR, iPR.
Step 3: iBOR of iSD If an iBOR of iSD is not determined, Step 4 will be performed.	At least one iSD assessment (or better), ≥ 6 weeks (≥ 42 days) after baseline; if not, at least one follow-up scan (i.e., consecutive scan) evaluated as iSD (or better) is required to determine an iBOR of iSD. If not consecutive scans, with no other assessment between the two determinations other than NE, iCR, iPR, iSD.
Step 4: iBOR of iCPD	At least one (i.e., any) iCPD after baseline.

If an iBOR of iCPD is not determined, Step 5 will be performed.	
Step 5: iBOR of iUPD If an iBOR of iUPD is not determined, Step 6 will be performed.	At least one (i.e., any) iUPD after baseline.
Step 6: iBOR of NE	Measurable disease at baseline, but not all or any target lesions have been evaluated, or if derivation of iBOR from Step 1 to 6 does not apply. Non-measurable disease at baseline will also result in iBOR of NE

The best overall response will be determined for all protocol specified assessments, i.e. scheduled assessments and also for all unscheduled assessments with non-missing information.

Confirmatory scanning ([Table 3](#)) for patients who have obtained PR or CR (or respectively iPR or iCR) is needed and should be approximately 4 weeks after the initial response.

Table 3 Confirmation CR and PR

Response: First Time Point	Subsequent Time Point	BOR
CR	CR	CR
CR	PR	SD, PD or PR (see comment*)
CR	SD	SD provided minimum criteria for SD duration met#, otherwise, PD
CR	PD	SD provided minimum criteria for SD duration met#, otherwise, PD
CR	NE	SD provided minimum criteria for SD duration met#, otherwise NE
PR	CR	PR
PR	PR	PR
PR	SD	SD
PR	PD	SD provided minimum criteria for SD duration met#, otherwise, PD
PR	NE	SD provided minimum criteria for SD duration met#, otherwise NE
NE	NE	NE

* Sometimes (i)CR may be claimed when subsequent scans suggest small lesions were likely still present and in fact the patient had (i)PR, not (i)CR at the first time point. Under these circumstances, the original (i)CR should be changed to (i)PR in the eCRF and the best response is (i)PR. If that is not the case, the (i)BOR of (i)SD will be determined considering two consecutive assessments better than (i)SD. This applies to both RECIST 1.1 and iRECIST..

At least one SD assessment (or better), \geq 6 weeks (\geq 42 days) after baseline; if not, at least one follow-up scan (i.e., consecutive scan) evaluated as SD (or better) is required to determine a BOR of SD. If not consecutive scans, with no other assessment between the two determinations other than NE, CR, PR, SD..

5.5.3.2. iORR

The iORR is defined as the proportion of patients with iCR or iPR. iORR will be analyzed in the efficacy population and presented as a point estimate along with 95% Clopper-Pearson CI. Patients with missing data will be considered as non-responders.

iORR analysis will be repeated for ASaT and PP populations and will be repeated in the efficacy population where patients with missing data will be excluded from the analysis.

ORR according to iRECIST will also be listed for the enrolled population.

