8.1.2 Tumor imaging during the study

The first on-study scan assessment should be performed at 6 weeks (± 2 weeks; starting from cycle 1 day 1). Subsequent tumor scans should be performed every 6 weeks (± 2 weeks).

All supplemental imaging must be collected.

Objective response should be confirmed by repeat scan performed at least 4 weeks after the first indication of a response is observed. Patients will then return to the regular scan scheduled, starting with the next scheduled time point. Patients who receive additional scans for confirmation do not need to undergo the next scheduled scan if it is fewer than 4 weeks later; scans may resume at the subsequent scheduled time point.

When radiological disease progression is identified by the investigator in clinically stable patients, disease progression is to be confirmed by another set of scans performed 4 to 8 weeks later, per iRECIST guidelines in section [8.1.5](#).

If disease progression is not confirmed, clinically stable patients are to continue study interventions until progression is confirmed. Patients are to return to their regular scan schedule. If the next scheduled scan will occur in less than 4 weeks, this scheduled scan may be skipped.

If disease progression is confirmed, study interventions will be discontinued. Exceptions are detailed in section [8.1.5](#).

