8.1.3 End of treatment and follow-up tumor imaging

If patients discontinue study interventions, tumor scans should be performed at the time of discontinuation (± 4 -week window) unless previous scans were obtained within 4 weeks of discontinuation.

If patients discontinue study interventions without documented disease progression, every effort should be made to monitor disease status by acquiring tumor scans using the same schedule used while on treatment (every 6 weeks [± 2 weeks]).

Scans are to be continued until:

- Confirmed disease progression per iRECIST

- Start of next-line anti-cancer treatment
- Pregnancy of the patient
- Withdrawal of consent by the patient
- End of the study

All imaging assessments need to have confirmatory imaging using the identical method after at least 4 weeks.

Patients who are clinically stable and treated past radiographic progression may continue to be assessed until progression is confirmed according to the rules of iRECIST, when clinically appropriate.

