5.5.3.4. CBR and iCBR

The CBR and iCBR are defined as the number of PR, iPR, CR, iCR, and SD, iSD and will be analyzed in the efficacy population and presented as a point estimate along with 95% Clopper-Pearson CI. SD, iSD needs to last at least 6 weeks from the start of study treatment; if not, at least one follow-up scan is required to declare stable disease. Patients with missing data will be considered as non-responders.

The analysis will be repeated for ASaT and PP populations as well as in the efficacy population where patients with missing data will be excluded from the analysis.

CBR according to RECIST and iRECIST will be presented in a data listing for ASaT population.

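### The SAP's response steps contradict the protocol on the confirmation interval and contradict SAP 6.1 on when the stable-disease clock starts

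*SAP*

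**What the plan says.** **Confirmation interval.** Protocol 8.1.2 states "Objective response should be confirmed by repeat scan performed at least 4 weeks after the first indication of a response is observed", and Protocol 8.1.3 repeats the interval: "All imaging assessments need to have confirmatory imaging using the identical method after at least 4 weeks". SAP 5.5.3.1 assigns best overall response in ordered steps, and Step 2 asks for "At least two consecutive determinations of PR or CR, more than 4 weeks apart". Step 1 for CR, and Steps 1 and 2 of the iBOR table, set the same strict interval. The sentence introducing Table 3 says that confirmatory scanning "is needed and should be approximately 4 weeks after the initial response", with no tolerance. Table 3 itself maps PR followed by PR to PR without any interval. SAP section 6, which lists departures from the protocol, does not mention the interval.

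**Start of the stable-disease clock.** SAP 6.1 declares that the six-week minimum for SD and iSD runs from the start of treatment instead of from the baseline scan. The text above the step table agrees, and so does SAP 5.5.3.4: "SD, iSD needs to last at least 6 weeks from the start of study treatment; if not, at least one follow-up scan is required". Step 3 of the BOR table instead reads "At least one SD assessment (or better), ≥ 6 weeks (≥ 42 days) after baseline". Step 3 of the iBOR table reads "At least one iSD assessment (or better), ≥ 6 weeks (≥ 42 days) after baseline", and the Table 3 footnote keeps "42 days) after baseline; if not, at least one follow-up scan".

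**The concern.** The step tables are what a programmer will code, and on both points they differ from the rule stated elsewhere.

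The interval matters because SAP 5.5.1 derives the primary ORR from BOR, so Steps 1 and 2 decide who is a responder. The strict and inclusive readings differ at one gap only, exactly 28 days, which is exactly four weeks. The looser wording above Table 3 opens a difference in the other direction, since it could admit gaps shorter than 28 days.

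The SD start point matters for BOR, iBOR, CBR and iCBR. SAP 4.1.2 defines baseline as the last value before first dose, and 6.1 contrasts the baseline scan with the start of treatment, so baseline in Step 3 cannot readily be read as the first dosing day. The change declared in 6.1 did not reach the tables that carry it out.

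In an open-label trial, leaving either choice to the programming stage means it could be made after the data have been seen.

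**Working it through.** The plan states no figure that depends on these definitions, so there is nothing of its own to reproduce. All days below are elapsed days since first dose, as in the tumor windows of SAP 4.1.4, not the SAP's study-day numbering.

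**Inputs**
- N = 52 and desired ORR 36.8% (Protocol 9.5): 0.368 × 52 = 19.1, so 19 responders serve as the example.
- First scan 28 to 56 days after first dose, second 70 to 98 (every 6 weeks ± 2 weeks, Protocol 8.1.2).
- Baseline scan 0 to 21 days before first treatment (Protocol 9.3.1).
- Assumption: dates are uniform over whole days within each window.

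**1. Confirmation interval**

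| Gap (days) | Protocol (≥ 28) | SAP Steps 1–2 (> 28) |
|---|---|---|
| 27 | not confirmed | not confirmed |
| 28 | confirmed | not confirmed |
| 29 | confirmed | confirmed |

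Let a be the first scan and b the second. The gap b − a = 28 requires a between 42 and 56, which gives 15 of 29 × 29 = 841 pairs, or 1.8%. Expected patients: 19 × 0.0178 = 0.34 at most, because a later PR or CR scan can still confirm the response. With scans within 7 days of nominal the share is 1/225 = 0.4%. Within 3 days it is 0/49.

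Protocol 8.1.2 also allows extra confirmation scans, which may be booked at exactly four weeks. If 5% of 19 responders were confirmed only that way (assumption), 0.95 patients are affected, or 0.95/52 = 1.8 points. At 10% it is 1.9 patients, or 1.9/52 = 3.7 points.

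One patient moves ORR by 1/52 = 1.9 points: 19/52 = 36.5% (Clopper-Pearson 95% CI 23.6–51.0) becomes 18/52 = 34.6% (22.0–49.1).

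For the looser wording above Table 3, gaps under 28 days make up 105/841 = 12.5% of pairs over the full windows. A tolerance of 3 days (assumption) would admit 39/841 = 4.6% that both other rules reject. With scans within 7 days of nominal, no gap is below 28 days.

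CBR is unaffected: two PR or CR scans that fail Steps 1 and 2 still satisfy Step 3 as SD.

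**2. Start of the SD clock**

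Let c be the age of the baseline scan at first dose. The two rules disagree when a < 42 and a + c ≥ 42.
- Full window: a = 28 allows 8 values of c, rising by one per day to 21 values at a = 41. The sum is 14 × (8 + 21)/2 = 203 of 29 × 22 = 638 pairs, or 32%.
- Within 7 days of nominal: 126/330 = 38%.
- Within 3 days: 60/154 = 39%.
- Every scan exactly 42 days after first dose: 0%.

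The 21-day limit follows Protocol 9.3.1. Protocol 8.1.1 times the initial scan before consent, so an older scan is conceivable and would raise these shares. Unscheduled scans also count towards BOR, so disagreement can begin before 28 days: a scan 21 days after dosing with a baseline scan 21 days before it reaches 42.

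Example: SD at 35 days, baseline scan 10 days before dosing. Step 3 as written gives 35 + 10 = 45 ≥ 42, so SD. Under SAP 6.1, 35 < 42, so the patient is PD if the next scan is PD, or NE if there is none. For iBOR the alternatives are iCPD, iUPD or NE. Each such patient moves CBR by 1/52 = 1.9 points.

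**The case against.** The strongest reply is that this is copy-editing. The interval conflict exists on a single day and touches a fraction of one patient under uniform dates. Table 3 would itself call a day-28 patient PR. Protocol 8.1.2 and 8.1.3 are imaging instructions, and the protocol's ORR definition (9.3.2) states no interval. No hypothesis test depends on the result. Under the plan's uniform prior, the posterior probability that ORR exceeds 28.8% is 0.899 at 19/52 and 0.837 at 18/52, both above 80%. The futility analysis is largely protected, because SAP 5.6.12 counts responses still awaiting a confirmatory scan. On SD, section 6.1 already states the intended rule, and the 32–39% figures are shares of date pairs, not of patients.

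Most of this stands as a limit on size. It does not remove either conflict. That Table 3 and Step 2 classify the same day-28 patient differently is a further inconsistency within the SAP. The protocol's imaging sections give its only confirmation interval, and the SAP declares no departure from it. Section 6.1 shows which SD rule was meant, but the tables that implement SD still contradict it.

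**Conclusion.** Both conflicts are in the current text and should be settled before database lock.

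The interval conflict reaches the primary endpoint but is small: at most 0.34 of 19 responders under uniform dates, more only if confirmation scans are booked at exactly four weeks. It can change BOR, iBOR, ORR and iORR, but not CBR.

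The SD conflict cannot change ORR. It can change BOR, iBOR, CBR and iCBR where an early scan of SD or better has no follow-up scan of SD or better. The documents do not allow that fraction to be estimated, so the 32–39% of date pairs is the share open to disagreement and not an expected number of reclassified patients.

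The percentages rest on the uniform-date assumption and the windows stated in the documents. The existence of the conflicts does not.

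**What to change.** In Steps 1 and 2 of both the BOR and iBOR tables, state the interval as at least 4 weeks (28 days), and use the same wording in the sentence introducing Table 3. In Step 3 of both tables and in the Table 3 footnote, count the 42 days from the start of study treatment, as SAP 6.1 declares. Leave the follow-up-scan alternative in Step 3 unchanged. If the strict interval is in fact intended, SAP section 6 should declare it as a departure from the protocol.

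The cost is a few words in the SAP before database lock, with no new data or analyses.

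### For an isolated, unedited CR followed by PR, SAP 5.5.3.1 gives PR under Step 2 and SD under the Table 3 comment, and ORR is taken from that result

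*SAP*

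**What the plan says.** SAP 5.5.1 ties the primary endpoint to BOR ("To determine the ORR, the BOR (see" Section 5.5.3.1), so whatever fixes BOR fixes responder status.

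SAP 5.5.3.1 then sets out BOR twice.

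- **Step tables.** Step 1 gives CR for "At least two consecutive determinations of CR more than 4 weeks apart". Failing that, Step 2 gives PR for "At least two consecutive determinations of PR or CR, more than 4 weeks apart, or if not consecutive", with only NE, CR or PR between the two. The iBOR steps are parallel.
- **Table 3 and its comment.** For CR followed by PR the outcome cell reads "SD, PD or PR (see comment", with an asterisk. The comment covers the case where later scans suggest small lesions were probably still present at the first time point: "the original (i)CR should be changed to (i)PR in the eCRF and the best response is (i)PR". It continues: "If that is not the case, the (i)BOR of (i)SD will be determined considering two consecutive assessments better than (i)SD". Its scope is explicit: "This applies to both RECIST 1.1 and iRECIST".

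No sentence gives either route precedence, and SAP Section 6, which records changes and clarifications to the planned analysis, does not mention the matter.

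**The concern.** Two programmers working faithfully from SAP 5.5.3.1 could code this sequence differently. One would count the patient in the ORR numerator and the other would not. The same choice decides whether the patient counts in iORR, enters the DoR analysis, and has an event in TtR.

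The planned ORR sensitivity analyses (Protocol 9.3.2, SAP 5.5.2) vary only the population and the handling of missing data, so none would reveal the difference. If the choice is left until data are in hand, it will be made in an open-label, single-arm trial with the affected patients visible.

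**Working it through.** **Step 1: apply both rules to the same sequences.** Scans are nominally every 6 weeks (Protocol 8.1.2), so consecutive scheduled scans are normally more than 28 days apart. Days are from the start of treatment.

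| Sequence | Step tables | Table 3 and comment |
|---|---|---|
| CR day 42, PR day 84, PD day 126; CR not edited | PR | SD |
| CR day 42, PR day 70, PD day 126; CR not edited | SD (28 days is not more than 4 weeks) | SD |
| CR day 42, PR day 84, PR day 126; CR not edited | PR | PR, if the PR/PR row is applied to the later pair |
| PR day 42, CR day 84, PR day 126, PD day 168 | PR | PR (PR/CR row) |
| CR day 42 changed to PR in the eCRF, PR day 84 | PR | PR |

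Only the first row conflicts. CR then PR fails Step 1, meets Step 2 and stops there as PR, with no edit required. The comment's second branch addresses exactly that unedited pair and gives SD. It therefore cannot be read as merely explaining Step 2.

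**Step 2: the PD entry.** The Table 3 footnote on SD duration is satisfied by a follow-up scan rated SD or better. A PR after a CR is such a scan, so the SD criterion is always met for this pair. PD cannot be reached from it, and the comment names no condition for PD.

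**Step 3: reproduce the plan's figures.** Inputs: N = 52, minimal ORR 28.8%, desired ORR 36.8%, uniform prior (SAP 2.3); futility if r < 2 of 16 by an exact 80% CI (SAP 5.6.12).

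- Posterior with r responders: Beta(1 + r, 53 − r). The desired rate gives 52 × 0.368 = 19.1 expected responders. At r = 19, P(ORR > 28.8%) = 0.899, consistent with the stated minimum of 80%.
- Clopper-Pearson 80% CI: 1/16 gives 0.7% to 22.2%, which excludes 28.8%; 2/16 gives 3.4% to 30.0%, which includes it. The boundary r < 2 is reproduced.

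**Step 4: effect of one reclassified patient.**

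- Final ORR: 1/52 = 1.92 percentage points.
- 19 to 18 responders: ORR 36.5% to 34.6%; 95% CI 23.6–51.0% to 22.0–49.1%; posterior 0.899 to 0.837.
- 18 to 17 responders: posterior 0.837 to 0.755, either side of the 80% used for sizing.
- Interim, 2 to 1 responders of 16: upper 80% limit 30.0% (continue) to 22.2% (futile). SAP 5.6.12 counts unconfirmed responses for ongoing patients whose confirmatory scan is pending. A patient whose second scan already shows PR is not clearly covered.

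These are one-patient illustrations. The documents give no CR rate from which to forecast how many patients will be affected.

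**The case against.** The strongest reply is that the conflict is narrow and the plan already has safeguards. Most of that stands.

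- A reader might infer that every CR followed by PR is affected. The table above shows otherwise: four of its five sequences get the same answer either way, one of them provided the PR/PR row is applied to the later pair.
- A reader might infer that the comment lets a site turn a non-responder into a responder at will. The comment is directive: it says when the CR should be changed. Protocol 10.1.7 requires a dated, attributed and reasoned audit trail that preserves the earlier entry. Protocol 10.1.8 requires full verification of primary data, and Protocol 8.1 has all scheduled scans collected. Local judgement enters every response in this trial. What is missing is a stated deadline and a listing for these corrections.
- A reader might infer that SD is the right answer. Table 3 is the text specific to this sequence, which favours SD. But Protocol 8.1.2 asks for objective response to be confirmed by a repeat scan at least 4 weeks later, and a PR after a CR arguably does that, which favours Step 2. The documents do not settle it.
- A reader might set 1.9 points against the 8.0-point gap between 28.8% and 36.8%. That gap is a sample-size input. No formal test is planned (Protocol 9.1), and the final result is an estimate with a wide CI.

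None of this says which rule to program for the one conflicting sequence.

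**Conclusion.** The contradiction is certain on the text and reaches the primary endpoint. It is a conflict between two stated rules, not a missing detail. It applies when all of these hold: CR is the first response, PR follows more than 4 weeks later, the CR has not been changed in the eCRF, and no other pair confirms response.

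Each such patient moves ORR by 1.9 points, taking the planned 52 as the denominator. The number of such patients is unknown and probably small; 0 to 2 is an assumption, giving 0 to 3.8 points (2/52). The PD entry in the same cell has no route in either derivation. Resolving this before database lock is worth doing because it is cheap and settles responder status in advance.

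**What to change.** Before database lock, state one rule for CR then PR and use it in the BOR steps, the iBOR steps and Table 3.

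- **If Table 3 governs:** add an exception to Step 2 (BOR and iBOR) that a single uncorrected CR followed by PR does not by itself confirm PR. Keep confirmation for sequences with two CRs or with a later PR/PR or PR/CR pair. Restricting Step 2 to PR/PR and PR/CR pairs would go too far. CR day 42, CR day 70, PR day 126 fails Step 1, because the CRs are exactly 28 days apart, and is PR under the present Step 2; it would become SD.
- **If Step 2 governs:** change the Table 3 cell to PR and delete the SD branch of the comment.

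In either case, remove PD from the cell or state its condition. Require any CR-to-PR correction to be made before database lock, and list those corrections from the existing audit trail. Report ORR under the other rule if any patient is affected. A separate ORR on assessments as first entered is not needed; it would also undo legitimate corrections.

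Cost: SAP wording, one programming rule and a short listing. ORR may be slightly lower if Table 3 governs.
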